9.6.1.3 Overall Survival

The nonparametric Kaplan-Meier method [Kaplan, E. L. 1958] will be used to estimate the survival curves. The treatment difference in survival will be assessed by the stratified log-rank test in participants with CPS ≥ 1 and in participants with CPS ≥ 20 . A Cox proportional hazard model with Efron's method [Efron, B. 1977] of tie handling will be used to assess the magnitude of the treatment difference (ie, the HR). The HR and its 95% CI from the Cox model with a single treatment covariate will be reported. The stratification factors used for randomization (Section 6.3.2) will be applied to both the stratified log-rank test and the stratified Cox model. Participants without documented death at the time of analysis will be censored at the date of last known contact.

9.6.1.4 Duration of Response

For participants with a CR or PR, whichever occurs first, censoring rules for DOR are summarized in [Table 12](#). DOR will be assessed using RECIST 1.1 by BICR.

For each DOR analysis, a corresponding summary of the reasons for which responding participants are censored will also be provided. Responses in participants who are alive, have not progressed, have not initiated new anticancer treatment, and have not been determined to be lost to follow-up, and who have had a disease assessment within approximately 5 months of the data cutoff date, are considered ongoing at the time of analysis. If a participant meets multiple criteria for censoring, the censoring criterion that occurs earliest will be applied.

If the sample size permits, DOR will be summarized descriptively using Kaplan-Meier medians and quartiles. Only the subset of participants with a confirmed CR or PR will be included in this analysis.

Table 12 Censoring Rules for Duration of Response

Situation	Date of Progression or Censoring	Outcome
No progression nor death, no new anticancer therapy initiated	Last adequate disease assessment	Censor (non-event)
No progression nor death, new anticancer therapy initiated	Last adequate disease assessment before new anticancer therapy was initiated	Censor (non-event)
Death or progression immediately after ≥ 2 consecutive missed disease assessments or after new anticancer therapy, if any	Earlier date of last adequate disease assessment prior to ≥ 2 missed adequate disease assessments and new anticancer therapy, if any	Censor (non-event)
Death or progression after ≤ 1 missed disease assessments and before new anticancer therapy, if any	PD or death	End of response (Event)
PD progressive disease. A missed disease assessment includes any assessment that is not obtained or is considered inadequate for evaluation of response.		

9.6.1.5 Analysis Strategy for Key Efficacy Endpoints

Table 13 summarizes the analysis strategy for the primary and secondary efficacy endpoints.

Table 13 Analysis Strategy for Key Efficacy Variables

Endpoint/Variable	Statistical Method	Analysis Population	Missing Data Approach
Primary Analyses			
OR/ORR (RECIST 1.1 by BICR)	Test and estimation: Stratified Miettinen and Nurminen method.	ITT	Participants with missing data are considered nonresponders.
Secondary Analyses			
PFS (RECIST 1.1 by BICR)	Summary statistics using Kaplan-Meier method Estimation: stratified Cox model with Efron's tie-handling method	ITT	Censored according to rules in Table 11 .
DOR (RECIST 1.1 by BICR)	Summary statistics using Kaplan-Meier method	All responders in ITT	Censored according to rules in Table 12 .
OS	Summary statistics using Kaplan-Meier method Estimation: stratified Cox model with Efron's tie-handling method	ITT	Censored at last known alive date.
BICR blinded independent central review; DOR duration of response; ITT intention to treat; ORR objective response rate; OS overall survival; PFS progression free survival; RECIST 1.1 Response Evaluation Criteria in Solid Tumors Version 1; iRECIST modified RECIST 1.1 for immune based therapeutics. Sensitivity analyses will be performed for ORR, PFS, and DOR using RECIST 1.1 and iRECIST based on investigator's assessment.			

9.6.2 Statistical Methods for Safety Analysis

There are no safety hypotheses for this study. Safety and tolerability will be assessed by clinical review of all relevant parameters, including AEs, laboratory tests, and vital signs.

The analysis of safety results will follow a tiered approach ([Table 14](#)). The tiered approach will be used for the comparisons of Arm 1 versus Arm 2. The tiers differ with respect to the analyses that will be performed. AEs (specific terms as well as system organ class terms) and events in laboratory, vital sign, and ECG parameters are either prespecified as Tier 1 events or will be classified as belonging to Tier 2 or Tier 3 based on the percentage of events observed.

Tier 1 Events

Safety parameters or AEOSIs that are identified a priori constitute Tier 1 safety events that will be subject to inferential testing for statistical significance.

AEOSIs that are immune-mediated or potentially immune-mediated are well documented and will be evaluated separately; however, these events have been characterized consistently

throughout the pembrolizumab clinical development program and determination of statistical significance is not expected to add value to the safety evaluation. Based on review of historic data from ongoing MK-1454 and pembrolizumab clinical studies, there are no known AEs associated with participants for which determination of a p-value is expected to impact the safety assessment. Therefore, there are no Tier 1 events for this protocol.

Tier 2 Events

Tier 2 events will be assessed via point estimates with 95% CIs provided for differences in the proportion of participants with events using the Miettinen and Nurminen method, an unconditional, asymptotic method [Miettinen, O. and Nurminen, M. 1985].

Membership in Tier 2 requires that at least 10% of participants in any treatment arm exhibit the event. The threshold of at least 10% was chosen because participants enrolled in this study are in critical condition and usually experience various AEs of similar types regardless of treatment, events reported less frequently than in 10% of participants would obscure the assessment of the overall safety profile and add little to the interpretation of potentially meaningful treatment differences. In addition, Grades 3 to 5 AEs ($\geq 5\%$ of participants in one of the treatment arms) and SAEs ($\geq 5\%$ of participants in one of the treatment arms) will be considered Tier 2 events. Because many 95% CIs may be provided without adjustment for multiplicity, the CIs should be regarded as a helpful descriptive measure to be used in safety review, not a formal method for assessing the statistical significance of the between treatment differences.

Tier 3 Events

Safety events that are not Tier 1 or Tier 2 events will be considered Tier 3 events. Only point estimates by treatment arm will be provided for Tier 3 safety parameters.

Continuous Safety Measures

For continuous measures such as changes from baseline in laboratory, vital sign, and ECG parameters, summary statistics for baseline, on-treatment, and change from baseline values will be provided by treatment arm in table format.

Table 14 Analysis Strategy for Safety Parameters

Safety Tier	Safety Endpoint	95% CI for Treatment Comparison	Descriptive Statistics
Tier 2	Any AE ($\geq 10\%$ of participants in one of the treatment arms)	X	X
	Any Grades 3 to 5 AE ($\geq 5\%$ of participants in one of the treatment arms)	X	X
	Any serious AE ($\geq 5\%$ of participants in one of the treatment arms)	X	X
Tier 3	Any AE		X
	Any change from baseline results (laboratory tests, vital signs, ECGs)		X

[figure not shown]
AE adverse event, CI confidence interval; ECG electrocardiogram

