4 STUDY DESIGN

4.1 Overall Design

This is a randomized, active-controlled, parallel group, multicenter, open-label, Phase 2 study of IT MK-1454 in combination with pembrolizumab versus pembrolizumab monotherapy in participants with a histologically or cytologically confirmed diagnosis of metastatic or unresectable, recurrent HNSCC with a tumor CPS ≥ 1 [Kulangara, K., et al 2018] as first-line

treatment. Participants need to have at least 1 measurable lesion that is amenable to IT injection for RECIST assessment.

This study will evaluate the efficacy, safety, and tolerability of IT MK-1454 in combination with pembrolizumab IV versus pembrolizumab IV alone. Figure 1 depicts a summary of the study design. Approximately 200 participants will be randomized 1:1 using IRT to receive IT MK-1454 at a dose of [CCI] in combination with pembrolizumab (Arm 1) or pembrolizumab monotherapy (Arm 2). Randomization will be stratified by PD-L1 expression level defined by CPS (≥ 1 to < 20 vs ≥ 20), ECOG performance status (0 vs. 1) and tumor HPV status (positive, negative). In Arm 1, study intervention will be IT MK-1454 [CCI] administered Q1W for 6 weeks, then Q3W, in combination with pembrolizumab 200 mg IV Q3W. In Arm 2, study intervention will be pembrolizumab 200 mg IV Q3W.

After a screening period of up to 28 days, participants will be randomized 1:1 to Arm 1 or Arm 2. Participants may be treated for up to 35 cycles (approximately 24 months) after initiation of treatment with pembrolizumab alone or in combination with MK-1454. Discontinuation Follow-Up will be 30 days after the last dose.

Participants will be treated until PD, unacceptable toxicity, or other protocol-specified criterion for cessation of treatment, at which point they will be discontinued from the study intervention. Participants who discontinue study intervention will have posttreatment follow-up for disease status (including imaging) until PD, initiating a new anticancer therapy, withdrawing consent for study participation, or becoming lost to follow-up. This protocol does not allow participants to cross over to the other arm if they experience progression.

After confirmed PD, each participant will be followed up for safety at 30 days after the EOT, then will be contacted by telephone every 12 weeks (84 ± 7 days) for survival until death, end of the study, withdrawal of consent to participate in the study, or becoming lost to follow-up, whichever occurs first.

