8.4 Adverse Events, Serious Adverse Events, and Other Reportable Safety Events

The definitions of an AE or SAE, as well as the method of recording, evaluating, and assessing causality of AE and SAE and the procedures for completing and transmitting AE, SAE, and other reportable safety event reports can be found in Appendix 3.

AEs, SAEs, and other reportable safety events will be reported by the participant (or, when appropriate, by a caregiver, surrogate, or the participant's legally authorized representative).

The investigator and any designees are responsible for detecting, documenting, and reporting events that meet the definition of an AE or SAE as well as other reportable safety events. Investigators remain responsible for following up AEs, SAEs, and other reportable safety events for outcome according to Section 8.4.3.

The investigator, who is a qualified physician, will assess events that meet the definition of an AE or SAE as well as other reportable safety events with respect to seriousness, intensity/toxicity and causality.

8.4.1 Time Period and Frequency for Collecting AE, SAE, and Other Reportable Safety Event Information

All AEs, SAEs, and other reportable safety events that occur after the consent form is signed but before intervention randomization must be reported by the investigator if the participant is receiving placebo run-in or other run-in treatment, if the event cause the participant to be excluded from the study, or is the result of a protocol-specified intervention, including but not limited to washout or discontinuation of usual therapy, diet, or a procedure.

- All AEs from the time of intervention randomization through 30 days following cessation of study intervention must be reported by the investigator.
- All AEs meeting serious criteria, from the time of intervention randomization through 90 days following cessation of study intervention or 30 days following cessation of study intervention if the participant initiates new anticancer therapy, whichever is earlier, must be reported by the investigator.

- All pregnancies and exposure during breastfeeding, from the time of intervention randomization through 120 days following cessation of study intervention, or 30 days following cessation of study intervention if the participant initiates new anticancer therapy must be reported by the investigator.

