9.4.2 Safety Endpoints

Safety endpoint is the number/proportion of participants with AEs, and who discontinue study treatment due to AEs. In addition, safety and tolerability will be assessed by clinical review of all relevant parameters including AEs, laboratory tests, and vital signs.

A description of safety measures is provided in Section 8.3 Safety Assessments.

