9.12 Extent of Exposure

The extent of exposure will be summarized as duration of treatment in number of cycles or administrations as appropriate. Summary statistics will be provided on extent of exposure for the APaT population.

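### Arms are compared on AEs only by crude proportions, although time at risk depends on outcome; a time-aware comparison should be added beside them

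*Combined protocol and SAP*

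**What the plan says.** Section 9.4.2 defines the measure: "Safety endpoint is the number/proportion of participants with AEs, and who discontinue study treatment due to AEs". Section 9.6.2 then states that "Tier 2 events will be assessed via point estimates with 95% CIs provided for differences in the proportion of participants with events". The intervals come from the Miettinen and Nurminen method. For everything below Tier 2, "Only point estimates by treatment arm will be provided for Tier 3 safety parameters". An AE enters Tier 2 if at least 10% of either arm has it; for Grade 3 to 5 AEs and for SAEs the threshold is 5% (Table 14). The same section says there are no safety hypotheses and no Tier 1 events, and that the intervals are a descriptive aid to safety review.

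Time at risk is set elsewhere. Section 4.1: "Participants will be treated until PD, unacceptable toxicity, or other protocol-specified criterion for cessation of treatment", and "Participants may be treated for up to 35 cycles (approximately 24 months". Section 8.4.1: "All AEs from the time of intervention randomization through 30 days following cessation of study intervention must be reported by the investigator". For SAEs the window runs "from the time of intervention randomization through 90 days following cessation of study intervention", or 30 days if new anticancer therapy starts, whichever is earlier.

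Section 9.12 adds: "Summary statistics will be provided on extent of exposure for the APaT population". It does not link exposure to AEs. The readable text contains no person-time rate, time-to-first-event or fixed-window AE analysis.

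**The concern.** The period in which an AE can be recorded is time on treatment plus a fixed tail, and time on treatment depends on how the participant fares. If one arm stays on treatment longer, it has more time to accumulate events even when the monthly risk is the same. If one arm stops all study intervention early, a higher monthly risk can be masked.

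Two outputs are affected. One is the size of the Tier 2 difference. The other is which events get a between-arm interval at all, because Tier 2 entry is itself a crude percentage. Safety and tolerability is a secondary objective (Section 3). The synopsis lists no data monitoring committee, and an internal committee reviews accumulating safety data for decision-making (Section 10.1.4.1). A reader of these tables would want to know how much of a difference is time at risk.

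**Working it through.** The plan gives no figure for the safety comparison and no exposure assumption by arm, so there is no stated value to reproduce. What follows is an illustration.

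**Inputs from the documents.** The earlier pembrolizumab trial in Section 2.2.3.2 had a median exposure of 3.5 months in its monotherapy arm, used here for Arm 2. The same section reports AE proportions of 20% (rash, constipation) and 33% (fatigue) on monotherapy. The tail is 30 days, about 1 month (Section 8.4.1). Allocation is 1:1 with about 200 participants.

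**Assumptions.** The AE hazard λ is constant and the same in both arms. Time on treatment is exponential. Arm 1 median exposure is 5.0 months (longer) or 1.75 months (half).

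**Formula.** With μ = ln 2 / median exposure, P(event) = 1 − e^(−λ) × μ/(μ + λ).

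1. Arm 2: μ = 0.693/3.5 = 0.198. Setting P = 0.20 gives λ = 0.0398 per month. Check: 1 − 0.961 × 0.198/0.238 = 0.20.
2. Arm 1 at 5.0 months: μ = 0.1386, P = 1 − 0.961 × 0.1386/0.1785 = 25.4%.
3. Arm 1 at 1.75 months: μ = 0.396, P = 1 − 0.961 × 0.396/0.436 = 12.7%.
4. Capping treatment at 24 months changes these only to 25.1% and 12.7%.
5. For a 33% event the same steps give 40.1% and 22.2%.

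**SAE window.** With a 3-month tail, 20% becomes 24.1% at 5.0 months and about 15% at 1.75 months. The longer tail softens the effect but does not remove it.

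**Tier 2 entry.** At 5.0 months an 8% event reaches 10.6%, and a 4% Grade 3 to 5 event reaches 5.4%. Each crosses its threshold with no difference in hazard.

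**A true excess (24-month cap).** Take a 1.5-fold hazard in Arm 1 and a 20% event in Arm 2. The crude difference is +7.7 points at equal exposure, but −1.8 points if Arm 1 median exposure is halved.

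**Scale against precision.** With 100 per arm and 20% in both, the 95% interval is ±11.2 points. A shift of 5.4 points (25.4 − 20.0) is about half that half-width. In a more extreme case (24-month cap, 33% event, Arm 1 median 7.0 months) the shift is +14.0 points, interval +0.4 to +27.1.

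**Where the effect vanishes.** If all risk falls in the first 6 weeks, a 20% event stays between 19.7% and 20.2% for Arm 1 medians from 1.75 to 7.0 months.

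**Limits of person-time rates.** In that same front-loaded case, equal risk gives a rate ratio of 0.76 at 5.0 months, a false advantage for Arm 1. A true 1.5-fold hazard shows as 1.20, while the crude proportions show about 29% against 20%.

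**Limits of a 12-week window.** Twelve weeks is about 2.76 months, so collection is still open if treatment lasted beyond 1.76 months. The share is e^(−1.76μ): 71% at a median of 3.5 months, 78% at 5.0 and 50% at 1.75. The early window narrows the imbalance but does not remove it, so the end of collection needs a stated rule.

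**The case against.** The strongest objection is that nothing in the plan is wrong. The proportion of participants ever having an event under the regimen as given is a legitimate measure of burden and is the endpoint that Section 9.4.2 defines. The intervals are declared descriptive, no decision rule in the readable text depends on them, and the Section 9.12 table would reveal an exposure imbalance. This stands, and it limits the point to an addition. A reader might infer that the crude comparison fails the safety objective; the documents do not support that. It answers the objective in part. An exposure table shows an imbalance but does not yield a comparison at equal exposure.

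A reader might also infer that the design expects longer exposure in Arm 1 because it assumes ORR of 40% against 19%. The documents state no exposure or PFS assumption by arm, so longer Arm 1 treatment is plausible only, and the direction is open. The 5.8-month median in Section 2.2.3.2 comes from the earlier trial's chemotherapy combination and is no guide to Arm 1.

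Further, MK-1454 is given weekly for six doses and then every 3 weeks, and its managed reactions (injection site, cytokine release) may well come early. For those, crude proportions are nearly unaffected and a person-time rate can dilute real toxicity. This stands and decides the order of the remedy. Finally, Section 6.6.1 allows MK-1454 to be held while pembrolizumab continues, which keeps the AE window open. Understatement therefore arises mainly when all study intervention stops early.

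**Conclusion.** The point holds as a gap in the safety analysis, not as an error. For events that accrue over time, outcome-dependent exposure can move the crude between-arm difference, and the Tier 2 threshold, without any difference in risk. Under a constant, equal hazard and a 3.5-month Arm 2 median, the shift for a 20% event is about +5 points at an assumed 5.0 months in Arm 1 and about −7 points at an assumed 1.75 months. For events confined to the first weeks it is close to nil. These sizes rest on assumed Arm 1 exposures, exponential treatment duration and reference figures from an earlier trial; the real sign and size are unknown until exposure is seen. ORR power and type I error are not touched. A time-aware comparison is worth prespecifying because it is cheap. The supplemental SAP is described as covering exploratory and nonconfirmatory analyses, so it cannot be assumed to contain one.

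**What to change.** Keep the crude proportions in Section 9.6.2 and Table 14. For Tier 2 events, Grade 3 to 5 AEs, SAEs and discontinuations due to an AE, add:

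1. The cumulative incidence of first event by arm, with the between-arm difference and 95% CI at a fixed early time such as 12 weeks. State how death and the end of AE collection are handled (competing event or censoring).
2. As a supportive measure, first-event rates per 100 person-months by arm, with the between-arm difference and 95% CI.

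Person-time should follow each event type's own collection window, counted from the last dose of any study intervention: 30 days for AEs; 90 days for SAEs, or 30 if new anticancer therapy starts. A single 30-day cut for all events would discard SAE data that the protocol collects.

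The cost is SAP text and a few table columns from data already collected. There are two cautions to write in. The rates assume a roughly constant hazard and can dilute front-loaded injection-site or cytokine-release events, so they must be read beside the early-window estimate. Arm 1 has weekly visits in the first two cycles and Arm 2 does not, so a possible ascertainment difference should be noted with the 12-week result.

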Tumor Imaging, RECIST 1.1, iRECIST, and/or itRECIST Response Assessment							X	X	Tumor imaging (CT or MRI) and medical photography (for cutaneous lesions) to be performed 6 weeks (42-49 days) after the first dose, and then every 6 weeks (42 days ± 7 days) for the first year, then every 9 weeks (63 days ± 7 days) thereafter. Imaging schedule should follow calendar days and should not be adjusted for delays in cycle starts. Continue imaging schedule until confirmed disease progression, discontinuation from study, or start of new anticancer treatment. Medical photography can be performed more often as medically warranted.

Study Period:	Combination Treatment Phase (3-Week Cycles)								Notes
Treatment Cycle/Title:	Cycle 1			Cycle 2			Cycle 3	Cycle 4 and Beyond	
Treatment Days:	1	8	15	1	8	15	1	1	
Scheduled Day and Window:	+3	±3	±3	±3	±3	±3	±3	±3	
Medical Photography (Cutaneous Lesions)							X	X	
Safety Procedures									
Directed Physical Examination	X			X			X	X	
Weight	X			X			X	X	
Vital Signs	X	X	X	X	X	X	X	X	Measure prior to study intervention. Vital signs include heart rate, respiratory rate, blood pressure, O ₂ saturation, and temperature.
ECOG performance status	X			X			X	X	Performed within 72 h prior to study intervention dosing on Day 1 of each cycle. Additional ECOG can be performed as clinically indicated.
12-Lead Electrocardiogram (Local)							X		
Pregnancy test – Urine or Serum β-hCG for WOCBP	X								Required within 24 h prior to first dose of study medication. Does not need to be repeated if screening pregnancy test was done within 24 h of the first dose of study medication on C1D1. If a urine pregnancy test cannot be confirmed as negative, a serum pregnancy test is required. Pregnancy testing must be done as required by local regulation. Refer to Appendix 7 for country-specific requirements.
Urinalysis	X			X			X	X	Required within 72 h of C1D1. Does not need to be repeated if screening labs were done within 72 h of C1D1. May be performed up to 72 h prior to dosing for subsequent cycles when scheduled.
CBC with Differential	X	X	X	X	X	X	X	X	
PT or INR and PTT or aPTT	X			X			X	X	
Chemistry Panel	X	X	X	X	X	X	X	X	PTT may be performed if the local lab is unable to perform aPTT. Any participant receiving anticoagulant therapy should have coagulation factors monitored closely throughout the study.
LDH, GGT	X			X			X	X	

Study Period:	Combination Treatment Phase (3-Week Cycles)							Notes
	Cycle 1			Cycle 2			Cycle 3	

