Tumor Imaging, RECIST 1.1, iRECIST, and/or itRECIST Response Assessment			X	X	Tumor imaging (CT or MRI) and medical photography (for cutaneous lesions) to be performed 6 weeks (42-49 days) after the first dose, and then every 6 weeks (42 days ± 7 days) for the first year, then every 9 weeks (63 days ± 7 days) thereafter. Imaging schedule should follow calendar days and should not be adjusted for delays in cycle starts. Continue imaging schedule until confirmed disease progression, discontinuation from study, or start of a new antitumor treatment. Medical photography can be performed more often as medically warranted.
Medical Photography (cutaneous lesions)			X	X	

Study Period:	Treatment Phase (3-Week Cycles)				Notes
Treatment Cycle/Title:	Cycle 1	Cycle 2	Cycle 3	Cycle 4 and Beyond	
Treatment Days:	1	1	1	1	
Scheduled Day and Window:	+3	±3	±3	±3	
Safety Procedures					
Directed Physical Examination	X	X	X	X	
Weight	X	X	X	X	
Vital Signs	X	X	X	X	Measure prior to study intervention. Vital signs include heart rate, respiratory rate, blood pressure, O ₂ saturation, and temperature.
ECOG performance status	X	X	X	X	Performed within 72 h prior to study intervention dosing on Day 1 of each cycle. Additional ECOG can be performed as clinically indicated.
12-Lead Electrocardiogram (Local)			X		
Pregnancy test – Urine or Serum β-hCG for WOCBP	X				Required within 24 h prior to first dose of study medication. Does not need to be repeated if screening pregnancy test was done within 24 h of C1D1. If a urine pregnancy test cannot be confirmed as negative, a serum pregnancy test is required. Pregnancy testing must be done as required by local regulation. Refer to Appendix 7 for country-specific requirements.
Urinalysis	X	X	X	X	Required within 72 h of C1D1. Does not need to be repeated if screening labs were done within 72 h of C1D1. May be performed up to 72 h prior to dosing for subsequent cycles when scheduled.
CBC with Differential	X	X	X	X	
Chemistry Panel	X	X	X	X	
LDH, GGT	X	X	X	X	
Thyroid Function Testing (TSH, T3 [or FT3], T4 [or FT4])	X		X	X*	Total T3 and T4 are preferred over FT3 and FT4. Required within 72 h prior to Day 1 of C1, C3, C5*, C7, C9, C11, and at every other subsequent treatment cycle. Does not need to be repeated on C1D1 if screening labs were done within 72 h of C1D1. *Cycle 4 not required.
AE Monitoring	X				

Study Period:	Treatment Phase (3-Week Cycles)				Notes
Treatment Cycle/Title:	Cycle 1	Cycle 2	Cycle 3	Cycle 4 and Beyond	

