6.2.2.1 Timing for Administration for MK-1454

MK-1454 will be administered as an IT injection on Day 1, Day 8, and Day 15 of the first 2 cycles (Q1W for Cycles 1 and 2), then on Day 1 of every 21-day cycle (Q3W) from Cycle 3 onward.

On days when both MK-1454 and pembrolizumab are to be administered, MK-1454 will be administered within 0.5 to 4 h after completion of the pembrolizumab IV infusion.

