6.2.2.2 Timing for Administration of Pembrolizumab

Pembrolizumab will be administered as an IV infusion on Day 1 of each 21-day cycle after all predose study procedures and assessments have been completed, as detailed in Section 1.3.

The Pembrolizumab Pharmacy Manual contains specific instructions for dose preparation and administration.

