8.3.2 Vital Signs

The investigator or qualified designee will take vital signs at screening, prior to the administration of each dose of study intervention and during the follow-up period as specified in the SoA. Vital signs include heart rate, respiratory rate, O₂ saturation, blood pressure, and temperature.

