8.3.4.1 Laboratory Safety Evaluations (Hematology, Chemistry, and Urinalysis)

Laboratory tests for hematology, chemistry, and urinalysis are specified in Appendix 2.

Laboratory tests for screening should be performed within 7 days prior to the first dose of study intervention. An exception is hepatitis and thyroid serologies, which may be performed within 28 days prior to first dose. After Cycle 1, predose laboratory safety tests can be conducted up to 72 hours prior to dosing unless otherwise noted on the flow charts.

Laboratory test results must be reviewed by the investigator or qualified designee and found to be acceptable prior to administration of each dose of study intervention. Unresolved abnormal laboratory values that are drug-related AEs should be followed until resolution. Laboratory tests do not need to be repeated after the EOT if laboratory results are within normal range.

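### Weekly checks in Arm 1 against 3-weekly checks in Arm 2 can tilt the Tier 2 intervals for short-lived laboratory and vital-sign events

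*Combined protocol and SAP*

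**What the plan says.** **Dosing.** Under Section 6.2.2.1, "MK-1454 will be administered as an IT injection on Day 1, Day 8, and Day 15 of the first 2 cycles", and then once per cycle. Under Section 6.2.2.2, "Pembrolizumab will be administered as an IV infusion on Day 1 of each 21-day cycle".

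**Checks tied to dosing.** Section 8.3.2 has site staff "take vital signs at screening, prior to the administration of each dose of study intervention". Section 8.3.4.1 requires laboratory results to be reviewed and "found to be acceptable prior to administration of each dose of study intervention". The schedules match this. Section 1.3.2 (Arm 1) marks vital signs, CBC and chemistry on Days 1, 8 and 15 of Cycles 1 and 2. Section 1.3.3 (Arm 2) marks them on Day 1 only. Section 1.3.2 also has a per-cycle row for PT/INR and PTT/aPTT, and Section 1.3.3 has none.

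**Analysis.** Section 9.6.2 sorts AEs, and also events in laboratory, vital-sign and ECG measures, into tiers by the percentage observed. An event seen in at least 10% of either arm is Tier 2, and "Tier 2 events will be assessed via point estimates with 95% CIs provided for differences in the proportion of participants with events", by the Miettinen and Nurminen method. Table 14 differs from this text: its Tier 2 rows name only AEs, and it puts change from baseline in laboratory tests, vital signs and ECGs in Tier 3, without an interval. Neither place limits the comparison to visits shared by the arms or mentions unequal assessment. The only caution on the intervals concerns multiplicity.

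**The concern.** The Tier 2 comparison counts whether a participant ever had the event. A short-lived abnormality is more likely to be found where more checks are made, so equal true rates can yield a higher observed percentage in Arm 1. Tier membership depends on the observed percentage, so extra checks can also decide whether an event gets an interval at all.

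Safety is a secondary objective, and the difference between arms will be read as the toxicity that MK-1454 adds. If part of it is detection, the reader should be told, and should have a figure that separates the two.

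Coagulation is a separate case. Section 9.5.2 admits a participant to the analysis of a laboratory parameter only with a post-dose measurement. Arm 2 has no scheduled on-treatment PT/INR or PTT/aPTT. Its denominator would therefore consist mainly of participants tested for clinical reasons, such as the anticoagulated participants whom Section 1.3.1 says to monitor.

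**Working it through.** The documents give no figure for safety ascertainment, so there is none to reproduce. The check counts scheduled visits, sets the true event process equal in both arms, and computes what would be detected.

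**Counts from Sections 1.3.2 and 1.3.3.** After the first dose, through Cycle 3 Day 1 (Day 43):

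- Arm 1: Days 8, 15, 22, 29, 36, 43, so 6 checks.
- Arm 2: Days 22, 43, so 2 checks.

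**Model A (assumed): independent probability p of an abnormality at each check, the same in both arms.** Detected proportion = 1 − (1 − p)^k for k checks. The intervals are Miettinen–Nurminen 95% on whole counts with 100 per arm (Section 9.9).

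| p | Arm 1, k = 6 | Arm 2, k = 2 | Artefact (points) | Counts | 95% CI (points) |
|---|---|---|---|---|---|
| 2% | 11.4% | 4.0% | 7.5 | 11 vs 4 | −0.4 to 15.2 |
| 5% | 26.5% | 9.8% | 16.7 | 26 vs 10 | 5.5 to 26.7 |
| 10% | 46.9% | 19.0% | 27.9 | 47 vs 19 | 15.2 to 40.0 |

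For p = 5%: 1 − 0.95^6 = 0.265 and 1 − 0.95^2 = 0.098. At p = 2%, only Arm 1 passes the 10% Tier 2 threshold, purely because of its schedule.

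**Longer follow-up.** The earlier pembrolizumab study described in Section 2.2.3.2 had a median monotherapy exposure of 3.5 months, about 5 cycles. Three further shared Day 1 checks give 9 against 5. The artefact becomes 7.0, 14.4 and 20.3 points for p = 2%, 5% and 10%. It is smaller than at week 6 but does not disappear.

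**Model B (assumed): one episode lasting D days, onset uniform over Days 1 to 43, true incidence 30% in both arms.** An episode is found if a check falls within it. Over the 42 days, Arm 1 finds a fraction 6 × min(D, 7)/42 and Arm 2 finds 2 × min(D, 21)/42.

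| D (days) | Arm 1 | Arm 2 | Difference on whole counts, 95% CI (points) |
|---|---|---|---|
| 3 | 12.9% | 4.3% | +9 (1.4 to 17.5) |
| 7 | 30% | 10% | +20 (9.2 to 30.9) |
| 14 | 30% | 20% | +10 (−2.1 to 21.9) |
| 21 | 30% | 30% | 0 (−12.7 to 12.7) |

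The artefact ends once an abnormality outlasts the 3-week gap between Arm 2 checks.

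**Shared visits only.** Counting only Day 1 of each cycle gives 2 against 2 checks through Cycle 3 Day 1, so the expected difference under equal true rates is 0. For example, 10 vs 10 of 100 gives a 95% CI of −8.8 to 8.8 points. The price shows in Model B: for a 7-day event with 30% true incidence, Day 1 checks find only 10%.

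**The case against.** Several points against the concern are sound.

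- **Which intervals are planned.** Table 14 gives intervals only to AEs. An interval for a laboratory or vital-sign event rests on the 9.6.2 text. This stands, and it is why text and table need aligning.
- **Descriptive status.** There are no safety hypotheses and no Tier 1 events, and Section 9.6.2 calls the intervals descriptive. No type I error is at stake. But the stated reason is multiplicity, and a descriptive estimate can still mislead.
- **Assumed rates.** No document supports the per-check rates or episode lengths. Independence between checks in the same participant also favours a large artefact. The figures show a range of possibilities and are not a forecast.
- **Weekly visits belong to the Arm 1 regimen.** True, and a reason to keep the all-visit analysis. It does not separate drug effect from detection.

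A reader might infer that AE rates in general are distorted in the ratio 6:2. The documents do not support that. Section 8.4.1 sets the same AE reporting window in both arms, and Section 8.4.2 prefers questioning the participant, which can pick up events between visits. A laboratory or vital-sign result becomes an AE only if the investigator judges it clinically significant (Section 10.3.1). Some AEs that originate in a laboratory finding may carry part of the effect. Nothing in the documents shows that an AE can be traced to the check that found it.

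A reader might also conclude that Day 1 counts should replace the main analysis. That would discard findings from the visits around the weekly MK-1454 injections, and could hide real short-lived toxicity. Section 2.2.3.1 gives a half-life of about 1.5 hours, so such toxicity is plausible.

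**Conclusion.** The point holds for laboratory and vital-sign events lasting under about 3 weeks, drawn from CBC, chemistry and vital signs. For these, the Tier 2 intervals that the 9.6.2 text allows can mix drug effect with detection frequency. Under equal true rates, the illustrative artefact by week 6 runs from 7.5 to 27.9 points for assumed independent per-check probabilities of 2% to 10%. It is zero for abnormalities lasting 21 days or more. Symptomatic AEs and SAEs should be little affected. This is a problem of interpretation in a descriptive analysis. The documents do not show that the toxicity of MK-1454 will in fact be overstated.

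On coagulation, it would go too far to say that Arm 2 has no data. Screening tests are done in all participants, and anticoagulated participants are monitored in either arm. What Arm 2 lacks is a scheduled on-treatment measurement, and that is enough to make a between-arm interval uninformative.

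**What to change.** In Section 9.6.2 and Table 14:

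1. Keep the all-visit analysis as the main one.
2. For laboratory and vital-sign events, add a supportive between-arm 95% CI restricted to the Day 1 visits scheduled in both arms.
3. State that the all-visit difference for these events includes unequal ascertainment.
4. Report coagulation results by arm descriptively, with no between-arm CI.
5. Make the text on laboratory and vital-sign events agree with Table 14 on which of them receive an interval.
6. Do not restrict AE counts to Day 1 visits.

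The cost is SAP wording and a few extra tables from data already collected. Participant monitoring does not change. The common-visit interval uses fewer Arm 1 measurements and can miss short-lived toxicity, so it should be labelled supportive only.
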